2.1.1.2 Visit and analysis window

Since the actual visit for a subject may not exactly coincide with their targeted visit date, the actual visit date is mapped to a study visit.

The nearest study day window will be utilized to define study visit for lab, vital signs, ECG and PROs collected during office visits before dose is administered.

2.1.1.3 Demographics and other baseline characteristics

Patient demographic and baseline characteristic data have been collected on all patients including: age, sex, race, relevant medical history/current medical condition present before signing informed consent for trial CAMG334ADE01 (HER-MES). These data from HER-MES trial will also be included in the analyses described in this SAP.

Prior headache characteristics and previous headache medication history prior to treatment in trial CAMG334ADE01 (HER-MES), including information on the suitability for migraine prophylactics will be collected as part of baseline characteristics.

Relevant medical history/current medical conditions present before signing the Informed consent for trial CAMG334ADE03 (APOLLON) will be recorded on the 'Medical History' eCRF page. Medical history and adverse events from the HER-MES trial represent medical history in APOLLON trial.

Novartis	Confidential	Page 11 of 34
SAP v1.1		CAMG334ADE03

Prior and concomitant medication in APOLLON trial will be recorded on the 'Prior/concomitant medication/non-drug therapies' eCRF page. Ongoing medication from HER-MES will be taken over on the APOLLON eCRF page 'Ongoing concomitant medication/non-drug therapies from HER-MES'. All concomitant medication from the HER-MES trial will be taken over as prior resp. concomitant medication. A comparison between the data records takes place to filter out duplicate entries.

2.1.1.4 Safety endpoints

Safety summaries (tables, figures) include only data from the on-treatment period with the exception of baseline data which will also be summarized where appropriate (e.g. change from baseline summaries). In addition, a separate summary for death including on treatment and post treatment deaths will be provided. In particular, summary tables for adverse events (AEs) will summarize only on-treatment events, with a start date during the on-treatment period (treatment-emergent AEs).

Discontinuation of treatment due to AE during the Treatment Epoch

Discontinuation of treatment due to AE during the Treatment Epoch is determined by the flag on the Treatment Completion eCRF page. "Death" as a reason for treatment discontinuation will be also included in AEs leading to treatment discontinuation.

Treatment-Emergent Adverse Event (TEAE)

Treatment emergent adverse events are defined as AEs occurred on or after the first dose of study treatment. AEs registered prior and after the first dose of study treatment are considered as treatment emergent if they have increased severity based on preferred term any time after the first dose of study treatment.

In case of missing data on a day of AE start date, the AE is considered as treatment emergent if *date of first dose of study treatment* \leq *latest possible start date*

Please, see section 5.1.2 AE date imputation for "latest possible start date" definition.

Serious Adverse Event (SAE)

SAEs are determined by the flag on the Adverse Events eCRF page.

Treatment-Related Adverse Event

Treatment-emergent adverse event is defined as treatment-related, if investigator considered it as having a reasonable possibility to be related to study treatment, which is reflected in the eCRF with a corresponding flag.

Adverse Event leading to dose adjustment

Adverse event is defined as leading to dose adjustment if at least one of the following actions was taken with the study treatment due to AE:

- dose increased
- dose reduced
- drug interrupted
- drug withdrawn

Novartis	Confidential	Page 12 of 34
SAP v1.1		CAMG334ADE03

Duration of exposure to IMP

For all calculations of exposure, dose date refers to receiving dose > 0. The duration of exposure to IMP is computed as min (last IMP dose date + 27, EoS date) – first IMP dose date + 1 either including the time of drug holiday or excluding the time of drug holiday.

Subject Incidence

The subject incidence for a given event in a given period is defined as the number of subjects with at least one reported occurrence of the event divided by the number of subjects who entered that period. For subjects with multiple occurrences of the same event, the event will only be counted once per subject.

Novartis
SAP v1.1

2.2 Analysis sets

The **Safety Set (SAF)** comprises all subjects who received at least one dose of study treatment in the open-label treatment epoch of CAMG334ADE03.

The Full Analysis Set (FAS) is equivalent to the safety set.

The Interim Analysis Set (IAS) consists of all Patients from FAS with planned or conducted drug holiday documented up to cut-off date for interim analysis.

The **Drug Holiday Analysis Set (DHAS)** consists of all Patients from FAS with planned or conducted drug holiday.

2.2.1 Subgroup of interest

Subgroup analyses are planned only for the primary endpoint (see section 2.5.4 Sensitivity analyses).

Novartis	Confidential	Page 15 of 34
SAP v1.1		CAMG334ADE03

2.3 Patient disposition, demographics and other baseline characteristics

2.3.1 Patient disposition

Patient disposition will be based on all screened patients data.

A patient disposition summary will include number and percentage of patients, concerning

- Screening: A patient is defined as screened if signed informed consent is available
- Screening failure: A patient is defined as screening failure if he was screened but did not enter the treatment epoch

The number of patients within each of the analysis sets (FAS, SAF, IAS, DHAS) used in the study will be given.

2.3.2 Demographics and other baseline characteristics

Demographic and other baseline data collected in trial CAMG334ADE01 (HER-MES) will be summarized descriptively for all subjects using the FAS.

Patient demographic data includes age (years), sex, race, weight (kg), height (cm), BMI (kg/m2), aura and disease duration.

Baseline disease characteristics contain following information assessed at baseline (see section 2.1.1 General definitions for baseline definition):

- Monthly migraine days
- Monthly headache days
- Acute headache medication (none vs. migraine-specific vs. non migraine-specific)
- Prior prophylactic treatment failure status (naïve vs. prior prophylactic treatment failure)

2.3.3 Medical history

Relevant medical history/current medical conditions present before signing the Informed consent will be recorded on the 'Medical History' eCRF page. Medical history and adverse events from the HER-MES trial will be taken over as medical history.

General medical history data includes medical history term, which will be summarized by system organ class and preferred term in the MedDRA dictionary.

Medical history possibly contributing to liver dysfunction data includes medical history term, which will be summarized by system organ class and preferred term in the MedDRA dictionary.

2.4 Treatments (study treatment, rescue medication, concomitant therapies, compliance)

2.4.1 Study treatment / compliance

The analysis of study treatment data will be based on the SAF.

Novartis	Confidential	Page 16 of 34
SAP v1.1		CAMG334ADE03

A data listing and a summary of erenumab administered will be provided. The summary will include

- duration of exposure summarized descriptively, patients assigned to 70 mg or 140 mg erenumab dose will be analyzed together under one treatment arm erenumab
- number and percentage of patients with starting dose of 70 mg or 140 mg
- number and percentage of patients with dose reduction or dose increase and the corresponding reason

2.4.2 **Prior**, concomitant and post therapies

Prior and concomitant medication will be recorded on the 'Prior/concomitant medication/nondrug therapies' eCRF page. Ongoing medication from HER-MES will be recorded on the eCRF page 'Ongoing concomitant medication/non-drug therapies from HER-MES'. All concomitant medication from the HER-MES trial will be taken over as prior or concomitant medication.

The number and percentage of patients receiving rescue medications will be reported. The number and percentage of patients receiving concomitant medications and significant non-drug therapy will be summarized by ATC level 1 and preferred name (coded by WHO Anatomic Therapeutic Chemical classification [ATC]) and by treatment group.

The use of concomitant medications and significant non-drug therapy during the follow-up period will be summarized in the same way, in a separate table.

Data listings of rescue medications and concomitant medications and significant non-drug therapy will be provided.

2.5 Analysis supporting primary objective(s)

The primary aim of the study is to evaluate the long-term safety of 70 and 140 mg erenumab in patients with episodic or chronic migraine.

Analysis on primary endpoint should be done based on the Safety Set (SAF).

2.5.1 **Primary endpoint(s)**

The primary endpoint variable is the exposure adjusted incidence rate of AEs during the openlabel treatment epoch per 100 subject years.

2.5.2 Statistical hypothesis, model, and method of analysis

The primary analyses will be conducted dividing the number of AEs by the time under treatment and standardizing it per 100 person-years. Exact Pearson-Clopper confidence intervals for single proportions will be calculated in order to evaluate the precision of the estimated parameter. No formal hypotheses testing will be conducted.

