#### 6.1.4 **Treatment duration**

The planned duration of treatment is 128 weeks for individual patients. However, each patient is eligible to one voluntary treatment interruption of up to 24 weeks (approximately 6 months) after an initial treatment duration of at least 12 weeks. After such a voluntary treatment interruption within the 128 weeks of the Treatment Epoch patients may return to the treatment schedule.

Subjects can be discontinued from treatment earlier due to unacceptable adverse events and/or at the discretion of the investigator or the subject.

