# 10 Safety monitoring and reporting

# 10.1 **Definition of adverse events and reporting requirements**

#### 10.1.1 Adverse events

An adverse event (AE) is any untoward medical occurrence (e.g. any unfavorable and unintended sign [including abnormal laboratory findings], symptom or disease) in a subject or clinical investigation subject after providing written informed consent for participation in the study. Therefore, an AE may or may not be temporally or causally associated with the use of a medicinal (investigational) product.

Novartis	Confidential	Page 42
Clinical trial protocol V01	Protocol No. CAMG334ADE03	_

The investigator has the responsibility for managing the safety of individual subject and identifying adverse events. Novartis qualified medical personnel will be readily available to advise on trial related medical questions or problems.

The occurrence of adverse events must be sought by non-directive questioning of the subject at each visit during the study. Adverse events also may be detected when they are volunteered by the subject during or between visits or through physical examination findings, laboratory test findings, or other assessments.

Adverse events must be recorded under the signs, symptoms, or diagnosis associated with them, accompanied by the following information (as far as possible) (if the event is serious refer to Section 10.1.2):

1. The severity grade:mild: usually transient in nature and generally not interfering with normal activities

- moderate: sufficiently discomforting to interfere with normal activities
- severe: prevents normal activities

2. its relationship to the study treatment.

- Yes
- No

3. its duration (start and end dates) or if the event is ongoing, an outcome of not recovered/not resolved must be reported

4. whether it constitutes a SAE (see Section 10.1.2 for definition of SAE) and which seriousness criteria have been met

5. action taken regarding with study treatment. All adverse events must be treated appropriately. Treatment may include one or more of the following:

- Dose not changed
- Dose Reduced/increased
- Drug interrupted/withdrawn

6. its outcome

- a. not recovered/not resolved;
- b. recovered/resolved;
- c. recovered/resolved with sequelae;
- d. fatal; or unknown.

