2.1.1.1 Study dates

First IMP Dose Date

The first IMP dose date is the date on which a subject is administered the first dose of erenumab following screening. For subjects who are screened but no dose administration is documented, first IMP Dose Date is considered missing.

Last IMP Dose Date

The last IMP dose date for each subject is defined as the latest date of a dose administration.

Time under treatment

Time under treatment is defined as (Last IMP Dose Date + 28 – First IMP Dose Date) - Duration of treatment interruption due to drug holiday (if applicable).

Exposure-adjusted incidence rate of AE

Exposure-adjusted patient incidence rate of AE is defined as the total number of patients who reported an AE in a given time period of follow up divided by total patient-years of exposure in that period.

Total patient-years of exposure is defined as the sum of the duration of exposure from first IMP dose to the earliest of end-of-study date, end-of-OLTP date, or first report of event across all patients during the OLTP.

Study Day

Study Day 1 is defined as the first IMP dose date. For patients who are screened but not dosed after inclusion, Study Day 1 is defined as the date of screening visit.

Study Day is defined as the number of days from Study Day 1.
Before Study Day 1:
Study Day = (Date of Interest – Date of Study Day 1)

On or after Study Day 1: Study Day = (Date of Interest – Date of Study Day 1) + 1

Therefore the day prior to Study Day 1 is Day -1.

Drug holiday

Drug holiday is defined as a voluntary single treatment interruption of up to 24 weeks introduced after at least 12 weeks of treatment in the open-label Treatment Epoch.

After the "Planned date of last dose before drug holiday" starts a 28 day drug holiday initiation period, followed by the actual drug holiday period (see definitions below).

Drug holiday planned

Drug holiday is defined as planned if in the eCRF "Planned date of last dose before drug holiday" is not missing.

Drug holiday started

Drug holiday is defined as started if in the eCRF "Planned date of last dose before drug holiday" is not missing and lies at least 4 weeks before the cut-off date (regarding the interim analysis) resp. end of study date and up to day 28 after the "Planned date of last dose before drug holiday" no IMP application is documented.

Return to treatment after drug holiday

Patients are defined as returned after drug holiday if in the eCRF "Date of first dose after drug holiday" is not missing.

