
Completion of drug holiday

Patients are defined to have completed their drug holiday if they either returned after drug holiday (see below) or if they discontinued study treatment, i.e. date of first dose after drug holiday or date of discontinuation of study treatment or date of study completion/discontinuation is given.

Drug holiday initiation period

The drug holiday initiation period

is defined as the 28 days-interval after start of the drug holiday

initiation period.

Start of drug holiday initiation period

The start date of drug holiday initiation period is defined as date of "planned date of last dose before drug holiday" from the eCRF + 1.

Novartis	Confidential	Page 10 of 34
SAP v1.1		CAMG334ADE03

Start of actual drug holiday period

The start date of the actual drug holiday period is defined as date of "planned date of last dose before drug holiday" + 28.

Patient-level End of Study (EoS) Date

The end of study (EoS) date for each subject is defined as the last date on which the subject participated in the study. The date will be recorded on the Treatment / study Completion eCRF page (Date of study completion/discontinuation).

On-treatment period

The on-treatment period lasts from the date of first administration of study treatment to 84 days after the date of the last actual administration of study treatment.

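### The primary AE rate takes the drug holiday out of person-time but not out of the AE count, and a second, incompatible rate definition is left standing

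*SAP*

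**What the plan says.** **The primary formula.** SAP 2.5.2: "The primary analyses will be conducted dividing the number of AEs by the time under treatment and standardizing it per 100 person-years". Protocol 12.4.1 uses the same formula without defining the denominator. SAP 2.1.1.1 defines it as "Last IMP Dose Date + 28 – First IMP Dose Date) - Duration of treatment interruption due to drug holiday".

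**What is counted.** SAP 2.5.1: "The primary endpoint variable is the exposure adjusted incidence rate of AEs during the openlabel treatment epoch per 100 subject years". The holiday is part of that epoch. Protocol 6.1.4: "After such a voluntary treatment interruption within the 128 weeks of the Treatment Epoch patients may return to the treatment schedule". AEs are recorded throughout. Protocol 10.1.1: "The occurrence of adverse events must be sought by non-directive questioning of the subject at each visit during the study". Protocol Table 8-1 includes AE collection at the holiday visits V201–V20X.

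**A second rate.** Under a heading almost identical to the endpoint's name, SAP 2.1.1.1 says: "Exposure-adjusted patient incidence rate of AE is defined as the total number of patients who reported an AE in a given time period", divided by patient-years. That person-time runs "from first IMP dose to the earliest of end-of-study date, end-of-OLTP date, or first report of event across all patients during the OLTP". No holiday subtraction is stated.

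**Holiday dates.** SAP 2.1.1.1 separates a 28-day initiation period from the holiday proper: "The start date of the actual drug holiday period is defined as date of" the planned last dose plus 28 days. The public text gives no dates for the interruption that is subtracted.

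**On-treatment window.** It ends 84 days after the last dose in SAP 2.1.1.1 and 112 days after it in Protocol 12.5.2. Protocol 10.1.1 asks for at least eight weeks of AE monitoring after the last dose. SAP Section 4 lists only the interim analysis as a change from the protocol.

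**The concern.** A rate needs events and person-time drawn from the same intervals. Here the holiday leaves the denominator, while every visible counting rule keeps its AEs in the numerator. The endpoint spans the epoch, treatment-emergent AEs are those from the first dose onward (SAP 2.1.1.4), and the on-treatment period runs unbroken across the holiday. The resulting rate is too high, and more so as more patients take longer holidays.

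The two rate definitions differ in numerator (AEs against patients), in when person-time stops (not at an event, against at the first event) and in holiday handling. Two competent programmers could report different primary results, and a reader comparing this trial with others could not tell which quantity was shown.

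**Working it through.** **1. The plan's own figures.** Protocol Table 1 gives precision for n = 500. With 1.96 × √(p(1−p)/500), taking 95% two-sided since no level is stated, I get 4.02, 3.51, 3.13 and 2.63 percentage points for 70, 80, 85 and 90%. The table has 4.0, 3.5, 3.1 and 2.6, so it reproduces. It concerns the proportion of patients with any AE. The plan gives no expected value for the rate.

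**2. Completer without a holiday.** The last dose is at week 124 (Table 8-1 footnote). Time under treatment is 124 × 7 + 28 = 896 days, which is the 128-week epoch. The ratio is 1.00 and there is no mismatch.

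**3. Completer with a holiday.** AEs accrue over 896 days at a constant rate (assumed), while the denominator loses the holiday:
- 24 weeks, 168 days subtracted: 896/728 = 1.231
- 24 weeks from the last dose, only the 140 days after the initiation period subtracted: 896/756 = 1.185
- 12 weeks, 84 days subtracted: 896/812 = 1.103

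**4. All completers.** Let a share f take a full holiday (f assumed). The factor is 896/(896 − d × f), where d is the number of days subtracted.

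| f | d = 168 | d = 140 |
|---|---|---|
| 20% | 896/862.4 = 1.039 | 896/868 = 1.032 |
| 50% | 896/812 = 1.103 | 896/826 = 1.085 |

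If the AE rate off drug is half that on drug, the excess over a rate that leaves the holiday out of both parts is (896 − 84f)/(896 − 168f). This gives 879.2/862.4 = 1.019 at 20% and 854/812 = 1.052 at 50%. Against a rate with the holiday in both parts, the d = 168 column applies whatever the off-drug rate.

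**5. Patients who do not return.** SAP 2.1.1.1 counts a holiday as completed when treatment is discontinued. For such a patient, last dose + 28 already leaves out the time after the initiation period. With a last dose at week 12 and 24 weeks off, subtracting again gives 84 + 28 − 168 = −56 days. The words *if applicable* in the formula do not settle whether this subtraction is made.

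**6. The two definitions compared, no holiday.** I calibrate to 87% of patients with an AE in three years (Protocol 12.8.1) and follow patients for 896/365.25 = 2.453 years.
- Poisson: −ln(0.13)/3 = 0.680 per year, so both definitions give 68.0 per 100 patient-years.
- Gamma frailty with variance k: the AE rate is (0.13^(−k) − 1)/(3k). The first-event rate is the proportion with an AE over mean years to first event or end.
  - k = 0.5: 1.773/1.5 gives 118.2, against 0.833/1.001, which gives 83.2. The ratio is 1.42.
  - k = 1: 6.692/3 gives 223.1, against 0.845/0.837, which gives 101.0. The ratio is 2.21.

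The frailty variances are assumptions. The gap depends on how AEs cluster within patients.

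**7. Tail, only if the on-treatment window also governs the primary count.** Planned discontinuation is 4.2% + 22.2% = 26.4% (Protocol 12.8.2). I assume a mean stop at week 64 and fully observed tails. Person-time is 0.736 × 128 + 0.264 × 64 = 111.1 weeks per patient. The tail beyond +28 days is 8 weeks (84 days) or 12 weeks (112 days):
- Discontinuers: 0.264 × 8/111.1 = 1.9%, or 0.264 × 12/111.1 = 2.9%
- With completers' four follow-up weeks added (0.736 × 4 = 2.94): 4.6% or 5.5%

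**The case against.** The public SAP is incomplete. Section 2.14 is cited but not shown, and the drug holiday analysis set has no visible use, so a holiday rule may stand in text that was removed. This limits the claim to the visible text. Even so, the whole of 2.5 on the primary endpoint and the entry for time under treatment can be read, and neither restricts AE onset or points to such a rule.

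The upward bias is also conditional. If the patient-based definition governs, no holiday is subtracted and that mismatch disappears. This is correct: the bias belongs to SAP 2.5.2. It does not help the plan, because the other branch contradicts 2.5.2, and the unresolved choice may matter more than the holiday.

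The size may be modest. The 23% is a per-patient maximum. At 20% uptake the 3.9% is smaller than the sampling error on about 834 AEs (500 × 0.680 × 2.453 under Poisson), where 1.96/√834 is about 7%. This stands as a limit on importance, but sampling error does not excuse an avoidable systematic one.

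The 84- and 112-day windows govern the safety summaries, and nothing says they apply to the primary count. That also stands, and the tail figures are conditional for that reason. Finally, dropping holiday AEs from the primary rate would make it cover fewer events than the treatment-emergent tables. This is a fair cost of that option, and keeping the holiday in both parts avoids it.

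**Conclusion.** The concern holds. As written, SAP 2.5.2 divides AEs from the whole epoch by person-time with the holiday removed, and SAP 2.1.1.1 offers a different rate under nearly the same name without saying which is primary. The holiday excess is nil for completers without one and at most 23% for one with a full holiday. It is 3.2% to 10.3% across completers at 20% to 50% uptake of full holidays, with equal AE rates on and off drug. Uptake, holiday length and the off-drug rate are assumptions. The definition conflict ranges from nothing under Poisson to about twofold under the frailty assumptions shown.

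No hypothesis is tested and the holiday error overstates harm. It should be fixed for accuracy and comparability, but it does not hide a safety signal.

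**What to change.** 1. In SAP 2.1.1.1 and 2.5.2, keep one rate definition for the primary endpoint and rename or delete the other.
2. Count only AEs with onset in the intervals that supply the person-time: holiday in both or out of both, and the same tail in both. One option is first dose to last dose + 28 days without the actual holiday period, with holiday and post-treatment AE rates shown separately on their own person-time. If the holiday is kept in both, the primary count stays in line with the treatment-emergent tables across the holiday.
3. Define the subtracted interruption by start and end dates, including for patients who do not return.
4. Reconcile the 84- and 112-day windows with each other and with the AE collection period, say whether the window applies to the primary count, and list the change in SAP Section 4.

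The cost is SAP wording, one onset-period flag on the AE dataset and, if the holiday is excluded, two extra table columns. No new data are needed. The headline rate would fall slightly compared with SAP 2.5.2 as written.

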#### 12.8.1 **Primary endpoint(s)**

In the three-year open-label phase II study 20120178 the proportion of patients reporting at least one AE was 87%. Based on this finding the following event rates and precisions were calculated for the proposed 128-week trial for the primary endpoint in Table 1.

Sample size	Proportion any AE	Precision (+/-)
500	70%	4.0%
	80%	3.5%
	85%	3.1%
	90%	2.6%

Table 1: Proportion of event and precision primary endpoint: Any AE

In conclusion a study population of at least 500 patients was found to be sufficient for the primary endpoint with an adequate range in precision.

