2.5.4 Sensitivity analyses

The primary analysis will also be conducted within the subgroups defined by sex, disease severity (MMD/MHD) at baseline and prior prophylactic treatment failure status (naïve vs. prior treatment failures).

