2.12 Biomarkers

Not applicable

3 Sample size calculation

In general, the 750 subjects randomized for clinical trial CAMG334ADE01 will be eligible for participation in the open-label study. It is estimated that approximately 75% to 85% of the study population meaning 563~638 subjects will enroll in the open-label study thus allowing the collection of long-term safety, efficacy and quality of life data of a large group of patients.

In the three-year open-label phase II study 20120178 the proportion of patients reporting at least one AE was 87%. Based on this finding event rates and precisions were calculated for the proposed 128-week trial for the primary endpoint. In conclusion a study population of at least 500 patients was found to be sufficient for the primary endpoint with an adequate range in precision.

The calculation of effect size and precision for the secondary endpoints is based on the proportion of study discontinuation rates in the three-year open-label phase II study 2012017. 4.2% of 383 patients discontinued this trial due to adverse events. Effect size and precision for the proposed study with at least 500 patients were calculated. In conclusion a study population of at least 500 patients was found to be sufficient for the secondary endpoints with an adequate range in precision.

Novartis	Confidential	Page 22 of 34
SAP v1.1		CAMG334ADE03

4 Change to protocol specified analyses

Contrary to what was stated in the protocol, an interim analysis will be conducted. For details please refer to section 2.14 Interim analysis.

5 Appendix

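### The primary adverse-event rate per 100 patient-years is given a binomial interval, is defined in two incompatible ways, and is planned with the precision of a different quantity

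*SAP*

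**What the plan says.** - **Endpoint.** SAP 2.5.1: "The primary endpoint variable is the exposure adjusted incidence rate of AEs during the openlabel treatment epoch per 100 subject years". Protocol Table 2-1 and section 12.4.1 agree.
- **Estimator, first definition.** SAP 2.5.2, in the same words as Protocol 12.4.1, obtains it by "dividing the number of AEs by the time under treatment and standardizing it per 100 person-years". SAP 2.1.1.1 defines time under treatment as first dose to last dose plus 28 days, less any drug holiday.
- **Estimator, second definition.** Under a heading that carries the endpoint's name, SAP 2.1.1.1 says: "Exposure-adjusted patient incidence rate of AE is defined as the total number of patients who reported an AE", divided by patient-years that stop at the first event, the end of the open-label period or the end of study. No holiday is subtracted.
- **Interval.** SAP 2.5.2 and Protocol 12.4.1: "Exact Pearson-Clopper confidence intervals for single proportions will be calculated in order to evaluate the precision of the estimated parameter". No hypothesis is tested and no confidence level is stated.
- **Subgroups.** SAP 2.5.4: "The primary analysis will also be conducted within the subgroups defined by sex", among other factors, so the same method carries over.
- **Planned precision.** Protocol 12.8.1: "Based on this finding the following event rates and precisions were calculated for the proposed 128-week trial for the primary endpoint in Table 1". The finding referred to is that 87% of patients in a three-year study had at least one AE. SAP section 3 concludes that "a study population of at least 500 patients was found to be sufficient for the primary endpoint with an adequate range in precision".

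**The concern.** Clopper-Pearson inverts a binomial distribution. It needs a fixed number of independent trials, and at most one success in each. AEs per unit of time have neither property: a patient can have several, and the rate can exceed 100 per 100 patient-years. The interval is valid for what SAP 2.1.1.4 calls subject incidence, "the number of subjects with at least one reported occurrence of the event divided by the number of subjects who entered that period", but that is a different parameter from the primary endpoint.

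With no test planned, the primary result consists of a point estimate and this interval. Followed literally, the plan gives the rate no interval, one that is too narrow, or one that describes something else. The two definitions can also give different point estimates from the same data, so numerator, denominator and interval would all be left to whoever programs the tables.

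**Working it through.** **1. Reproduce Table 1.** Inputs: n = 500 and proportions of 70%, 80%, 85% and 90% (Protocol 12.8.1). Formula: 1.96 × √(p(1−p)/500).

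| p | Stated ± | Computed (points) | Relative to p |
|---|---|---|---|
| 70% | 4.0 | 4.02 | 5.7% |
| 80% | 3.5 | 3.51 | 4.4% |
| 85% | 3.1 | 3.13 | 3.7% |
| 90% | 2.6 | 2.63 | 2.9% |

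The table is the 95% normal-approximation half-width of a crude proportion. (At 90% confidence the first row would be 3.37.) The arithmetic is right, but person-time does not enter it.

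**2. Compare the two estimators.**

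| | SAP 2.5.2 / Protocol 12.4.1 | SAP 2.1.1.1 |
|---|---|---|
| Numerator | all AEs | patients with an AE |
| Denominator | time under treatment, net of holiday | time to first AE, end of open-label period or end of study |

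SAP 5.4.1 only points back to section 2.5, and SAP section 4 lists only the interim analysis as a change. Neither resolves the conflict.

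**3. Illustration at equal hazard.** Assumptions not in the documents: 500 patients all complete 128 weeks without a holiday, and the hazard is constant and the same for everyone.

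- T = 896/365.25 = 2.453 years; hazard = −ln(0.13)/3 = 0.680 per year.
- Patients with an AE: 500 × (1 − exp(−0.680 × 2.453)) = 406. Time to first event: 405.7/0.680 = 597 patient-years. Rate: 68 per 100 patient-years.
- Exact Poisson limits, χ²(0.025; 2x)/(2PY) and χ²(0.975; 2x+2)/(2PY) with x = 406: **61.6 to 75.0**, half-width 6.7, about 10% relative.
- Clopper-Pearson, x = 406, n = 597 patient-years: **64.1 to 71.7**, half-width 3.8. Simulated coverage at equal hazard is about 74%.
- Clopper-Pearson, 406/500 patients: **77.5% to 84.5%**. This is correct for the crude proportion and does not contain 68.

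**4. Counting all AEs.** Under the same assumptions the count is 500 × 0.680 × 2.453 = 834 in 500 × 2.453 = 1,227 patient-years, again 68 per 100. Exact Poisson: 63.5 to 72.8 (±4.7, about 7% relative). Because 834 exceeds 500, Clopper-Pearson with patients as n cannot be computed. Suppose instead 26.4% discontinue (4.2% + 22.2%, Protocol 12.8.2) at an exponential rate over the 128 weeks, and everyone still on treatment takes a full 24-week holiday from week 12. The expected count is about 571, still above 500. With patient-years as n, the interval fails once the rate passes 100 per 100 patient-years.

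**5. Patients with unequal rates.** The documents give no dispersion figure, so this shows a range only. Individual rates follow a gamma distribution with shape k and mean k(0.13^(−1/k) − 1)/3, which keeps 87% at three years. Half-widths are per 100 patient-years and allow for the heterogeneity.

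| | Equal hazard | k = 2 | k = 1 |
|---|---|---|---|
| First-event rate per 100 PY | 68 | 83 | 101 |
| All-AE rate per 100 PY | 68 | 118 | 223 |
| Half-width, first event | 6.7 | 9.1 | 12.6 |
| Half-width, all AEs | 4.7 | 9.5 | 21 |
| Poisson coverage, first event | 96% | 92% | 87% |
| Poisson coverage, all AEs | 94% | 79% | 56% |

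Coverage is from 3,000 simulated trials per scenario. A patient-level robust interval covered 94% to 96% throughout.

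**The case against.** The documents never name patient-years as the binomial denominator. The natural reading of a single proportion is patients with any AE over patients, which is also what Table 1 plans for and openly labels in its column heading. On that reading the interval is computable and valid, so the 74% coverage does not arise. That is fair as to emphasis: an interval for the wrong parameter is the likeliest outcome. But neither document says the interval is for the crude proportion, and if it were, the rate would have no interval at all.

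SAP 2.5.2 matches the protocol and is the operative section, so it could be taken to override the general definition in 2.1.1.1. That suggests where to start the repair, but the definition still carries the endpoint's own name and nothing subordinates it.

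The gap between the estimators has no documented size: at equal hazard both give 68, and the larger gaps rest on assumed values of k. This stands, so those figures show only that the estimates can diverge.

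Finally, Table 1 is correct for a proportion, enrolment is capped by the parent trial and no power is at stake. This also stands, and makes that part a labelling correction. At the expected 563 to 638 patients, the first-event relative half-width at equal hazard is 9.3% to 8.7%, a little better than at 500.

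**Conclusion.** The concern holds on all three counts. The interval method does not fit the primary parameter, the SAP contains two estimators that differ in both numerator and denominator, and the precision shown is for the crude proportion. The first two follow from the text alone and depend on no numerical assumption. They need correcting before database lock because they govern the whole primary result. Table 1 is the lesser part.

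At equal hazard, 500 patients and full follow-up, the rate is known to about ±10% (first event) or ±7% (all AEs), against the 2.9% to 5.7% relative precision that Table 1 gives for the proportion. These sizes are illustrative. They rest on a 95% level inferred from Table 1, a constant hazard and, for the wider values, assumed heterogeneity.

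**What to change.** 1. Reconcile SAP 2.1.1.1 with SAP 2.5.2 and Protocol 12.4.1, and state one primary numerator and one denominator, including how drug-holiday time is treated.
2. Replace the Clopper-Pearson sentence in both documents and state the confidence level.
   - If the first-event rate is chosen: *A two-sided 95% exact Poisson (chi-square) interval will be given for the rate per 100 patient-years, with a patient-level robust or bootstrap interval as a check for heterogeneity.*
   - If all AEs are counted: *A two-sided 95% negative-binomial, patient-level robust or bootstrap interval will be given for the rate per 100 patient-years.*
   - Use the same method in the subgroups of SAP 2.5.4.
3. Relabel Protocol Table 1 as precision for the crude proportion with any AE. Add the expected rate, its half-width per 100 patient-years and the assumptions, and align SAP section 3. The crude proportion can stay as a separately named summary with its Clopper-Pearson interval.

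Optionally, Clopper-Pearson intervals could be specified for the two discontinuation proportions in SAP 2.6.2, where they would be appropriate.

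The cost is revised wording in both documents and standard code. No patients are added, because enrolment depends on the parent trial's pool (Protocol 12.8). The stated relative precision becomes less favourable.
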